### Normality Assumption

To assess the robustness of the MMRM results to deviations from normality assumption, a sensitivity analysis for the raw number of migraine headache days (the total number of migraine headache days for each interval without normalization to 30-day period) will be conducted with a repeated measures negative binomial regression analysis fitted with SAS PROC GLIMMIX. The model will include treatment, month, and treatment-by-month interaction, as well as the continuous fixed covariates of baseline number of monthly migraine headache days and baseline-by-month interaction, log (number of compliant calendar days within each month/30) as the offset in the model. In case of non-convergence, baseline-by-month interaction may be excluded from the model.

### Definition of Episodic Migraine Headache

This sensitivity analysis is to assess the robustness of the primary results to the deviation of minor change in the definition of migraine (See Criteria C. below). It is implemented by repeating the primary analysis using the number of monthly migraine headache days derived based on the following definition of migraine, which aligns with migraine headache days definition in chronic migraine, but is considered relevant for the episodic population, as well.

A headache, with or without aura, of  $\geq 30$  minute's duration with both of the following required features (Criteria A and Criteria B):

Criteria A. At least 2 of the following headache characteristics:

- Unilateral location
- Pulsatile quality
- Moderate or severe pain intensity
- Aggravation by or causing avoidance of routine physical activity

AND

Criteria B. During headache at least one of the following:

- Nausea and/or vomiting
- Photophobia and phonophobia

OR

Criteria C. Patient takes a triptan or ergot derivative.

In other words, if [Criteria A and Criteria B] or [Criteria C] is satisfied, then it is considered as “MHD with Criteria C”.

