Diagnosis	Definition/Criteria
Migraine headache	
A headache, with or without aura, of ≥ 30 minutes duration with both of the following required features (A and B):
 
A. At least 2 of the following headache characteristics:
 
 • Unilateral location • Pulsatile quality • Moderate or severe pain intensity • Aggravation by or causing avoidance of routine physical activity 
AND
 
B. During headache at least 1 of the following:
 
 • Nausea and/or vomiting • Photophobia and phonophobia 
(Definition adapted from the IHS ICHD-3 beta)

Probable migraine headache	
A headache missing 1 of the migraine features in the IHS ICHD-3 beta definition such that 1 feature in criteria A is missing or 1 feature in criteria B is missing; that is, meet at least 2 A criteria and none of the B criteria, or meet 1 of the A criteria and at least 1 of the B criteria.

Migraine headache day	
A calendar day on which a migraine headache or probable migraine headache occurred.

Migraine headache attack	
Beginning on any day a migraine headache and/or a probable migraine headache is recorded, and ends when a migraine-free day occurs.

Non-migraine headache	
All headaches of at least 30 minutes duration not fulfilling the definition of migraine or probable migraine.

Non-migraine headache day	
A calendar day on which a non-migraine headache occurred.

Headache day	
A calendar day on which any type of headache occurs, (including migraine headache, probable migraine headache, and non-migraine headache).

Migraine headache days with abortive (acute) medication use	
Calendar days on which migraine or probable migraine occurs, requiring abortive (acute) medication.

Migraine headache days or headache days with abortive (acute) medication use	
Calendar days on which any types of headache occurs, requiring abortive (acute) medication.

Abbreviations: ICHD = International Classification of Headache Disorders; IHS = International Headache Society.

5. Study Design

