## 4. Study Objectives

### 4.1. Primary Objective

The primary efficacy objective is to test the hypothesis that at least one dose of LY2951742 (120 or 240 mg/month) is superior to placebo in the prevention of migraine headache in patients with episodic migraine. Superiority is defined as greater improvement for LY2951742 compared with placebo as measured by the overall mean change from baseline in the number of monthly migraine headache days during the 6-month double-blind treatment phase.

A migraine headache day is defined as any calendar day with a headache lasting longer than 30 minutes that meets the criteria for migraine or probable migraine (see endpoint definition in [Table CGAN. 5.1](#)).

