**Primary Measure: the Number of Monthly Migraine Headache Days**

The primary measure is the number of monthly migraine headache days. A migraine headache day is defined as a calendar day on which a **migraine or probable migraine** occurs.

The primary measure of the number of monthly migraine headache days will be summarized from the daily ePRO data for each patient in that period (including 30 days of daily data from the baseline period prior to randomization, 6 months of daily data during the treatment phase, and 4 months of daily data during the post-treatment phase).

The daily data will be aggregated, and the number of migraine headache days will be provided for each of the 30-day periods. In calculating the number of migraine headache days for each period, if the period is not equal to 30 days, the number of migraine headache days will be normalized by multiplying the number of migraine headache days by  $(30/x)$  where 'x' is the total number of non-missing diary days in the period.

For the baseline period (Visit 2 to Visit 3), once a patient becomes eligible before Visit 3 judged from the daily ePRO data (this is called **eligible day**), then all ePRO data after the eligible day to Visit 3 will be ignored.

Example: A patient has Visit 2 = 2016/Jan/1. He records diary on Jan/2 for his headache information on Jan/1. He records diary everyday (no missing data.) He records diary on Jan/31 for his headache information on Jan/30 which ends up as 5th migraine headache day during the baseline period (starting from Jan/1.) He becomes eligible for CGAN study (assuming all other eligibility conditions are met.) He goes to a site on Feb/ 4 (Visit 3) and gets 1st injection on the day. In this case **eligible day** is 2016/Jan/30. All diary data of Jan/1, Jan/2,..., Jan/30 will be used as baseline period data. All diary data of Jan/31, Feb/1, Feb/2, Feb/3 will be ignored. Diary data on Feb/4 (Visit 3) is used for Month 1 period data.

For the double blind period (SP III), Month 1 period data is based on headache information from Visit 3 up to on Visit 5 – 1 day. Month 2 period data is based on headache information from Visit 5 up to Visit 6 – 1 day. Month 3, to Month 6 will be defined similarly.

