#### **5.5.10.2. Sensitivity Analysis for Primary Outcome**

Several types of sensitivity analyses are planned to assess the robustness of deviations from the assumptions of primary analysis including the target population, missing data assumption, and normality assumption and the influence of slight change in the definition of episodic migraine prevention.

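### Does the MHD with Criteria C sensitivity definition quietly drop probable migraine, and does that spoil the check?

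*SAP*

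**What the plan says.** The primary measure counts calendar days with "migraine or probable migraine" (SAP 5.4.1). SAP 4.1 says the same, and Protocol Table CGAN.4.2 defines the migraine headache day as "A calendar day on which a migraine headache or probable migraine headache occurred".

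Among the sensitivity analyses, the introduction to SAP 5.5.10.2 lists "the influence of slight change in the definition of episodic migraine prevention". The subsection on the definition of episodic migraine headache says that it tests robustness of the "primary results to the deviation of minor change in the definition of migraine (See Criteria C. below"). Monthly days are to be "derived based on the following definition of migraine", a definition "which aligns with migraine headache days definition in chronic migraine". Criteria A and B follow, as in the migraine row of Table CGAN. 5.1, and then Criteria C, the taking of a triptan or ergot derivative. The closing line reads "In other words, if [Criteria A and Criteria B] or [Criteria C] is satisfied, then it is considered as" an MHD with Criteria C. Probable migraine is not mentioned anywhere in the subsection.

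**The concern.** Under Table CGAN. 5.1 a probable migraine either meets at least two A features with no B feature, or one A feature with at least one B feature. It can therefore never satisfy A and B together. If the closing rule is applied as it stands, a probable-migraine day counts only when a triptan or ergot was taken. The analysis would then differ from the primary one in two ways that pull in opposite directions, while the text names one.

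The worry is interpretive. If the two changes offset each other, agreement with the primary result could be taken to show that Criteria C hardly matters. If the results differ, the difference could not be credited to Criteria C alone. Two programmers could also build different variables from the same page.

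**Working it through.** The question is definitional, and the plan states no figure to reproduce. The check is a classification of headache days.

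**Inputs.** Types: M = migraine (A and B met), P = probable migraine, N = other headache, all from SAP Table CGAN. 5.1. Suffix 1 means a triptan or ergot was taken that day, 0 means not; M = M0 + M1. Criteria C is applied to headache days only, because the definition opens with a headache of at least 30 minutes.

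| Day type | Primary MHD | ICHD MHD | Criteria C, literal | Criteria C, probable migraine kept |
|---|---|---|---|---|
| M0, M1 | yes | yes | yes | yes |
| P0 | yes | no | **no** | yes |
| P1 | yes | no | yes | yes |
| N0 | no | no | no | no |
| N1 | no | no | **yes** | **yes** |

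**Differences in counted days.**

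- Literal − primary = (M + P1 + N1) − (M + P0 + P1) = N1 − P0
- Probable kept − primary = (M + P0 + P1 + N1) − (M + P0 + P1) = N1
- Probable kept − literal = P0
- Primary − ICHD = P0 + P1
- Literal − ICHD = P1 + N1
- Check: (P1 + N1) − (P0 + P1) = N1 − P0

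So the literal rule does make two opposing changes. The other reading makes one, which is the change the SAP describes.

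**Illustration (assumed values; the documents give none).** With M = 5, P0 = 2, P1 = 1, N1 = 2:

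- Primary = 5 + 2 + 1 = 8
- ICHD = 5
- Literal = 5 + 1 + 2 = 8
- Probable kept = 5 + 2 + 1 + 2 = 10

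The literal count equals the primary count although 2 + 2 = 4 days changed status. If P0 and N1 may each lie anywhere from 0 to 3 days, literal − primary runs from 0 − 3 = −3 to 3 − 0 = +3. Under the other reading the difference runs from 0 to +3.

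**What this does not show.** These are levels of days. The analysis compares arms on change from baseline. Let D(X) be the active-minus-placebo difference in mean change for day type X. Ignoring covariate adjustment, D(literal) − D(primary) = D(N1) − D(P0). Equal levels of N1 and P0 do not make D(N1) and D(P0) equal, so matching counts do not imply cancelling treatment effects. The documents give nothing from which D(N1) or D(P0) could be estimated, so neither size nor sign can be stated.

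**Which reading does the text favour?**

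- For keeping probable migraine: the SAP calls this a change in the definition of migraine. Criteria A and B repeat the migraine row of Table CGAN. 5.1, whereas the migraine headache day is a separate row built from migraine or probable migraine. Where the SAP drops probable migraine on purpose (ICHD migraine headache days, SAP 5.4.1), it says so.
- For the literal rule: the closing line attaches the day-level label directly to the A-and-B-or-C condition. The chronic-migraine definition given as the model might also exclude probable migraine, but it is not in these documents.

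The text leaves both open.

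**What is already planned.** SAP Table CGAN. 5.5 lists an MMRM in Study Period III for primary MHD, for ICHD MHD and for MHD with Criteria C. If the literal rule is used, primary against ICHD shows the effect of leaving out probable migraine, and Criteria C against ICHD shows the effect of adding triptan or ergot days.

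**The case for a change.** The best case for a change is that the text is ambiguous and clearing it up costs a sentence. The variable feeds the sensitivity analysis and a baseline summary (SAP 5.5.4). The SAP shows elsewhere that it knows how to state an exclusion. On the literal rule the description as a minor change is incomplete, and a reader could draw too much from agreement with the primary result.

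The ambiguity stands, and so does the size of the gap between readings, P0 days. It is also right that, under the literal rule, a difference from the primary result should not be put down to Criteria C alone.

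The rest does not carry. The mismatch exists on one reading only; with probable migraine kept, the rule and its description agree. The stated purpose is robustness of the primary result to an altered definition, not isolation of the effect of Criteria C, and a treatment effect that holds under either variable is useful evidence of that. The cancellation argument rests on assumed day levels rather than treatment differences.

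The possible edits gain little. Writing probable migraine into the rule may break the alignment with chronic migraine that the SAP gives as its reason, and this cannot be checked here. Leaving the rule and relabelling it only names comparisons whose models are already planned.

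**Conclusion.** No change to the plan follows. SAP 5.5.10.2 leaves open whether probable migraine counts in one sensitivity variable. The two readings differ by P0 days per month, a quantity the documents do not give. Whoever programs the variable must choose a reading, and either choice gives a valid robustness check of the primary result. The report can state which was used without any amendment.

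The primary analysis, its multiplicity control, the sample size and the data collected do not depend on the choice. No effect on the treatment difference or on the trial's conclusion has been shown. This conclusion rests on two things: the analysis stays supportive, as the SAP presents it, and Criteria C is applied to headache days, as the opening of the definition implies.

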### ANCOVA

Using LOCF imputation, the primary analysis is conducted with ANCOVA (without multiplicity adjustment) described in Section 5.5.1.1.

#### Baseline definition by IWRS based eligibility date

Instead of using ePRO eligibility date, the one by IWRS will be used for the primary analysis without multiplicity adjustment (by PROC MIXED).

### 5.5.10.3. Secondary and Exploratory Efficacy Analyses

Table CGAN. 5.5 summarizes planned efficacy analyses for Study Period III, Study Period III/IV, and Study Period IV. All response rates are derived from migraine headache days unless otherwise specified. There will be no multiplicity adjustment for statistical test except for the primary efficacy analysis.

If analysis results would be considered less informative, then such results may not be provided in CSR. For example, the change from baseline analysis for number of migraine headache days with triptan use, if baseline values (see Section 5.5.4) are less than 1 day for at least one of the arms, then these analysis may not be provided in CSR because the improvement (change from baseline) is difficult to evaluate.

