### 3. Revision History

The Statistical Analysis Plan (SAP) Version 1 was approved prior to first patient visit (FPV) and any unblinding of the study team. Version 2 was approved prior to the first unblinding.

Following topics are major updates from I5Q-JE-CGAN (CGAN) protocol. Corresponding SAP sections are also specified:

- PROTOCOL Section 4. Several analysis definitions were modified to align with I5Q-MC-CGAG (CGAG) study and I5Q-MC-CGAI (CGAI) (SAP [Table CGAN. 4.1](#), [Table CGAN. 4.2](#), and [Table CGAN. 4.3](#)):
  - Key secondary: The definition of “The overall mean change from baseline in the number of monthly **migraine headache days or headache days** requiring medication for the acute treatment of **migraine headache or headache** during the 6-month, double-blind treatment phase” was modified. It was intended to be the same analysis as “The overall mean change from baseline in the number of monthly **migraine headache days** requiring medication for the acute treatment of **migraine** during the 6-month double-blind treatment phase” in other secondary objective. Eventually the other secondary objective was deleted.
  - Other secondary: HCRU analysis method was changed from statistical models to simple descriptive statistics.
  - Exploratory: MSQ categorical analysis (Role Functional Preventive) was omitted.
  - Exploratory: MSQ categorical analysis (Emotional Functional domain) was omitted.
  - Exploratory: MSQ categorical analysis (Role Functional restrictive) definition was modified.
  - Exploratory: “allergic reactions or hypersensitivity” was deleted.
  - Exploratory: “To compare galcanezumab with placebo with respect to the proportion of migraine headache days or headache days requiring medication for the acute treatment of migraine headache or headache” was deleted.
- PROTOCOL Section 10.2. Safety Population and ADA follow-up Cohort were added to align with CGAG. Safety Population would be used for safety analysis and exposure, instead of ITT population to align with CGAG (SAP [Section 5.5.1.3](#)).

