- Section 5.5.10.2: Sensitivity analysis by IWRS eligibility day was added.
- Section 5.5.10.3: Table CGAN. 5.5 was updated with new analysis defined in other sections. The following general rule was added: If analysis results would be considered less informative, (e.g. change from baseline analysis with rare baseline events,) then such results may not be provided in CSR.
- Section 5.5.11.3: HCRU analysis was simplified.
- Section 5.5.11.4: PSMQ-M analysis was simplified.
- Section 5.5.12.1: FEAE baseline definition was updated to align with the other baseline definitions in this study.
- Section 5.5.12.1.1.1 Hypersensitivity events: The section name was changed from “Allergic/hypersensitivity events” to “Hypersensitivity events”. Definition of SMQ was updated. The hypersensitivity analysis in SP IV was omitted.
- Section 5.5.12.1.1.2: The section name was changed from “injection site reactions” to “adverse events related to injection sites”. Timing of injection AEs were updated to align with CGAN CRF (different from hypersensitivity events timing recorded in CGAN CRF). “Summary of Injection Site Reaction by Max Severity, by Anatomical Location” was added for a medical request. “Figure of duration of Injection Site related Adverse Events” was added.
- Section 5.5.12.1.3 Table CGAN. 5.6: For Temperature, unit and criteria were updated to fit Japan use. A shit table was deleted. To align with the other vital analysis, analysis patients population were updated for
  - Systolic BP, PCS High
  - Diastolic BP, PCS High

➤ Temperature

- Section 5.5.12.1.4: For ECG and heart rate, data exclusion criteria were omitted because the information was not captured in this study. In Table CGAN. 5.7, “>500msec” criteria was labeled as “PCS High” for QTcF and QTcLCTPB analysis. Definition of qualitative ECG baseline was added.
- Section 5.5.12.1.5: Hy’s law was modified.
- Section 5.5.12.1.6: ADA follow-up cohort analysis was added. A line plot was omitted.
- Section 5.5.13: Body weight subgroup was added. MHD 50% response rate analysis was added for the treatment resistant status subgroup.
- Section 5.7 Table CGAN. 5.10. Unblinding members and reasons were updated. CTPM was added.
- Section 5.8.1: TFLs for interim analysis were updated. In particular, immunogenicity related TFLs were out of scope for the interim.

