### 4.2. Secondary Objectives

#### 4.2.1. Key Secondary Objectives

Key secondary objectives listed in [Table CGAN. 4.1](#) reflect comparisons of each LY2951742 dose with placebo.

Table CGAN. 4.1 List of Key Secondary Objectives and Their Endpoints

Objectives	Endpoints
To compare LY2951742 with placebo with respect to 50% response rate	The proportion of patients with reduction from baseline $\geq 50\%$ in monthly migraine headache days during the 6-month double-blind treatment phase
To compare LY2951742 with placebo with respect to 75% response rate	The proportion of patients with reduction from baseline $\geq 75\%$ in monthly migraine headache days during the 6-month double-blind treatment phase
To compare LY2951742 with placebo with respect to 100% response rate	The proportion of patients with reduction from baseline =100% in monthly migraine headache days during the 6-month double-blind treatment phase
To compare LY2951742 with placebo with respect to change in functioning	Mean change from baseline in the Role Function-Restrictive domain score of the Migraine-Specific Quality of Life Questionnaire version 2.1 (MSQ v2.1) (average of Months 4, 5, and 6)
To compare LY2951742 with placebo with respect to change in use of acute (abortive) migraine treatment	The overall mean change from baseline in the number of monthly migraine headache days requiring medication for the acute treatment of migraine during the 6-month double-blind treatment phase
To compare LY2951742 with placebo with respect to change in global severity of the migraine condition	Mean change from baseline in the Patient Global Impression of Severity (PGI-S) score (average of Months 4, 5, and 6)

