**Table CGAN. 5.9 Unblinded members through CGAN Study**

Role	Reason	Data source for unblinding
Product Delivery personnel	To provide and manage Clinical trial materials	e-CTS
Clinical Laboratory Operations	To manage and track sample shipping	CLRM
Unblind Case Manager	To report SAE with unblinded information to EU authority	e-CTS
Data Movement	To transfer unblinded data at the timing of interim DBL (and final DBL)	source data of CLUWE

Abbreviations: CLRM = Clinical Laboratory Results Modernization; DBL = database lock; e-CTS = Enhanced Clinical Trials System; EU = European Union; GPS = Global Patient Safety; IWRS = interactive web-response system; PK/PD = pharmacokinetics/ pharmacodynamics; SAE = Serious Adverse Event.

The interim analysis will be conducted by selected unblinded study team members who do not have direct interaction with sites (Table CGAN. 5.10). These members will become unblinded after the interim database lock. All study personnel with direct interaction with sites are kept blinded to the interim analysis results.

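### The SAP lets secondary and exploratory efficacy results judged less informative be left out of the study report, with no closed criterion, no blinding condition and no duty to list what was omitted

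*SAP*

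**What the plan says.** SAP 5.5.10.3 opens by pointing to Table CGAN 5.5 as the list of planned efficacy analyses. It then says "There will be no multiplicity adjustment for statistical test except for the primary efficacy analysis", and next gives the omission rule: "If analysis results would be considered less informative, then such results may not be provided in CSR".

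One example follows. For the change from baseline in migraine headache days with triptan use, the analysis may be left out "if baseline values (see Section 5.5.4) are less than 1 day for at least one of the arms", because improvement from so low a start is hard to evaluate.

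The SAP Revision History records the same provision among the changes made for Version 2: "The following general rule was added: If analysis results would be considered less informative". It mentions rare baseline events there in brackets, again only as an example. This entry summarises the same rule and is not a second provision.

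The key secondary objectives in SAP 4.2.1 "reflect comparisons of each LY2951742 dose with placebo". All six endpoints appear in Table CGAN 5.5 and are analysed under 5.5.10.3.

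**The concern.** A reporting rule is safe when its trigger cannot depend on the treatment comparison. That requires a fixed criterion, a decision taken before the codes are opened, or full disclosure of what was left out. This rule has none of the three. Its trigger is an open judgement, and the object judged is the analysis result.

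The matter carries more weight because everything beyond the primary analysis is tested without multiplicity adjustment. Nominal p-values across several dozen related measures can be interpreted only against the full set of tests. If some results are left out on a judgement that could have been made after seeing them, the reported set may no longer represent the planned one. An omission made for a sound reason could not be told apart from one that was not.

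**Working it through.** The rule carries no operating figure other than the 1-day example. None of the sample size figures (451 patients, effect size 0.36, about 88% power) enters the point. The check is a count of scope and a comparison of sections.

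**1. Scope, from Table CGAN 5.5.**
- Rows with a repeated-measures (MMRM) analysis, including the primary: 44.
- Other rows: 3 descriptive resource-use (HCRU) rows, 1 weekly migraine-day row, 3 response-rate rows (50/75/100% together, 30%, distribution), 1 time to first 50% response, 1 maintenance of response, 2 time-to-event rows for Study Period IV, and 5 responder or satisfaction rows. 3 + 1 + 3 + 1 + 1 + 2 + 5 = 16.
- Total: 44 + 16 = 60.
- Remove the primary (1), the descriptive HCRU rows (3) and the response distribution, for which the SAP plans no comparisons (1): 60 − 5 = 55 rows with a treatment comparison. Some rows hold several endpoints, such as the MIDAS items.
- Key secondary comparisons within these: 6 endpoints × 2 doses = 12.

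**2. Is the criterion closed?** No. Both statements of the rule give baseline rarity only as an example. In the triptan example the text does not say whether the baseline value is a mean or a median, and omission stays optional even when the condition is met. No threshold is given for measures that are not day counts.

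**3. Must it be applied blind?** No.
- SAP 5.8.1 has all Study Period III efficacy and quality-of-life analyses conducted at the interim lock, so results exist before the report is written.
- SAP 5.7 says of the interim analysis team: "These members will become unblinded after the interim database lock". Table CGAN 5.10 lists the project statistician, analysts, medical staff and medical writer among them, with CSR preparation as part of the stated reason.
- The example needs baseline values for each arm, which cannot be seen without treatment codes.

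**4. Are key secondary endpoints exempt?** No exemption is written. The illustrated ground could not sensibly reach most of them. Response rates rest on baseline migraine headache days, which inclusion criterion [4] sets at 4 to 14, and PGI-S and MSQ are not day counts. The open wording is not confined to that ground.

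**5. Is disclosure required elsewhere?** Protocol 10.3.1 and SAP 5.5.1 require changes to analysis methods to be described and justified. A result left out under an SAP rule is not a change of method, so these clauses do not apply.

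**6. How does the SAP handle similar judgements?**

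| Judgement | Safeguard in the SAP |
|---|---|
| Which events are true hypersensitivity (5.5.12.1.1.1) | Medical review before unblinding |
| Important protocol deviations (5.5.3) | Determined before database lock |
| Preventive and acute treatments (5.5.8) | Medical review before database lock |
| Display of C-SSRS p-values (5.5.12.1.2) | Fixed count: at least 4 events in at least one group |
| Omission of efficacy results (5.5.10.3) | None |

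The omission rule is the only one of the five with neither a time limit nor a fixed threshold.

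**The case against.** The best defence is that the rule is a modest, permissive exception with an evident purpose. Table CGAN 5.5 contains measures likely to be sparse, such as ergot use or aura on non-migraine headache days, for which change from baseline says little. The only ground shown is baseline rarity, not the direction or significance of an effect. The rule was itself fixed early: "Version 2 was approved prior to the first unblinding". SAP 5.8.1 and 5.8.2 make it the default that analyses are conducted and carried into the final CSR. For some key secondary results other text points towards reporting: SAP 5.5.1 has the PGI-S and MSQ comparisons shown for both averaging periods, and 5.5.10.1 plans numbers needed to treat for the response rates.

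Most of this stands and limits how serious the point is. It does not close the gap. Approval before unblinding fixes the wording of the rule, not the later judgement made under it, and a default does not bind where a written exception applies.

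Three stronger readings are tempting, and the documents do not support them:
- A reader might infer that unblinded staff make the decision. The SAP does not say who decides or when. It shows only that those preparing the CSR are unblinded by then and that nothing requires a blinded decision.
- A reader might infer that omissions would be undetectable. Anyone holding Table CGAN 5.5 and the CSR can see which rows are missing. Only the reason could remain unstated.
- A reader might size the problem by expected chance findings: 55 × 2 × 0.05 = 5.5 under no effect on any measure. That number comes from unadjusted testing and is the same whether or not anything is omitted. It also counts both directions, so only about half, 5.5 / 2 = 2.75, would favour galcanezumab. It does not measure this defect.

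**Conclusion.** The point holds as a defect in the reporting rule. As written, SAP 5.5.10.3 permits secondary and exploratory efficacy results, key secondary endpoints included, to be left out of the CSR on an open judgement that may be made after the results are known, with no duty to list or explain the omission. The conclusion is about what the rule allows. It does not say that selective reporting is intended or will occur.

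Its size is one of scope: about 55 table rows and, within them, 12 key secondary comparisons formally fall under the rule. The documents give no baseline frequencies, so the number of rows that might be dropped, and any effect on the overall picture, cannot be calculated. The section heading suggests that the primary analysis lies outside the rule, and its step-down Dunnett control is untouched. No alpha, power or sample size changes. The sentence should be amended, but the primary conclusion of the trial does not depend on it.

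**What to change.** Either of two changes to SAP 5.5.10.3 is enough.

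1. Delete the sentence and its example, and state that every analysis in Table CGAN 5.5 is reported in the CSR or its appendix, with sparse measures confined to the appendix if preferred.
2. Replace it with a closed rule limited to rare-event measures. Apply one stated statistic to blinded baseline data pooled over arms, for example a pooled mean below 1 day per 30 days, before the interim database lock. Exempt the primary and key secondary endpoints, and list each omitted analysis with its reason in the CSR.

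If the interim lock has already taken place, only the first is available, since the second depends on a blinded decision.

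The cost is a few SAP sentences and some extra appendix tables. Most of the tables would exist anyway, because SAP 5.8.1 already requires the Study Period III analyses to be conducted. The sponsor also gains: a reasonable omission of a sparse measure could then be verified as such.
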